All participants (in both trial arms) will complete assessments at baseline (prior to randomisation), 6- and 12-months post-randomisation and will be given a choice of how these are completed. These assessments can be completed in a number of ways, face-to-face, online on a website, via telephone, via videoconferencing, or on paper via the post. Participants, parents/guardians, young people and key stakeholders will be invited to participate in semi-structured interviews to ascertain acceptability and their experience of

the parenting programme and being in the trial. We will interview a sample of those randomised to each arm of the trial.

Randomisation

Families will be randomised with equal probability to either the intervention or comparator arm using random permuted blocks (block size 4), stratified by local authority site. The statistician doing the analysis will be blind to the treatment allocation. As the families and practitioners are not blind to treatment allocation (as this would be impossible given the intervention), there is no issue in terms of predictability.

Sample size

Sample size calculations were conducted using R version 4.1.2 (2021-11-01), and the 'pwr' R package.

Parents/carers within the same family will be randomised to the same arm, making this a cluster RCT, given responses within the same family are potentially highly correlated. We might expect, based on our previous research with families and consultation with the TMG (Trial Management Group), an average cluster size within families of up to a maximum of 1.5 parents and a high degree of correlation among parents/carers from the same family, so also allow for an ICC=0.5 (Davé et al., 2008). Following Teerenstra et al. (2012), we also allow for a correlation between baseline and follow-up measures of primary outcome of $r=0.5$ (this is a conservative estimate based on published SDQ test-retest correlations between 0.74-0.84; Nowak et al., 2008). The sample size is then inflated to account for 20% of families being lost to follow-up at the 12-month post-randomisation follow-up time point.

Allowing for the above assumptions and an effect size to be detected of 0.35 with 90% power and a two-sided alpha of 0.05, a sample size of $N=412$ ($N_1=206$, $N_2=206$) is required.

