A moderation analysis will adjust the primary analysis with the inclusion of the moderator as a main effect and interaction between moderator and randomised group indicator. For example, the LD moderator analysis is as follows:

$$L1: Y_{ik} = \beta_{0k} + \beta_{1k} SDQ_BL_{ik} + \beta_{2k} local_authority_{ik} + \beta_{3k} LD_{ik} + r_{ik}, \quad r_{ik} \sim N(0, \sigma^2)$$

$$L2: \beta_{0k} = \gamma_{00} + \gamma_{02} TX_k + \mu_{0k}, \quad \mu_{0k} \sim N(0, \tau_2^2)$$

$$\beta_{1k} = \gamma_{10}$$

$$\beta_{2k} = \gamma_{20}$$

$$\beta_{3k} = \gamma_{30} + \gamma_{20}TX_k$$

where, Y_{ik} are the SDQ scores; SDQ_BL_{ik} are the baseline SDQ scores; TX_{ik} is the treatment/control variable indicator; $Local_authority_{ik}$ are indicator of local authority (strata); LD_{ik} is learning disability status; μ_{0k} is the random intercept term for family; and r_{ik} is the individual level variation.

In addition to interpreting the magnitude and statistical significance of interactions, plots of the interactions will also be examined. These analyses will be hypothesis generating in nature only (i.e., will not be confirmatory and only indicate whether further research targeting the intervention may be warranted).

Missing data

Exploring the impact of missing data on the primary trial outcome by investigating likely missing data mechanisms and re-fitting the primary outcome within a multiple imputation framework (including exploring MAR and MNAR mechanisms via delta-based controlled multiple imputation).

We will summarise the extent of missing data in all outcomes and their respective control variables. A full multiple imputation strategy will be used if more than 5% of data in the primary model is missing. Alternatively, we will impute if more than 10% of data for a single variable is missing. We will use the multiple imputation by chained equations approach via the mice package in R (Van Buuren and Groothuis-Oudshoorn, 2011) and generate 10 imputed datasets. We will then estimate the intervention effect for each imputed dataset and pool the results using Rubin's combination rules for standard errors.

Missing data in item level data

The sum scores will not be imputed directly. Any missing item level data will be imputed using the chained equation approach. Each item's imputation model will use other items and covariates specified in the primary analysis model as predictors.

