Following creation of the imputed datasets, the corresponding total scores will be calculated using the imputed item level data. All imputed datasets will then fit the primary and secondary models and pool estimates following Rubin's rules (Rubin, 2004; van Buuren, 2018).

Primary outcome

Given that each item is an ordered category, we will use an ordinal regression within the imputation model for each item.

Secondary outcome Similarly, the correct link function will be used according to the item's structure for each of the secondary outcomes, i.e. binary or ordered categorical accordingly. Therefore, a logistic or ordinal model will be used in the imputation for these items.

Additional analyses

Longitudinal followup analyses (12 month only) – Primary outcome

We will fit linear mixed models, accounting for repeated post-randomisation measures (6- and 12-months post-randomisation) within participants, adjusting for local authority to investigate the overall effect of the intervention on post-randomisation measures.

$$L1: Y_{ijk} = \beta_{0jk} + \beta_{1jk}time_{ijk} + r_{ijk}, \quad r_{ijk} \sim N(0, \sigma^2_{|X})$$

$$L2: \beta_{0jk} = \gamma_{00k} + \mu_{0jk}, \quad \mu_{0jk} \sim N(0, \tau_2^2)$$

$$\beta_{1jk} = \gamma_{100} + \mu_{1jk}, \quad \mu_{1jk} \sim N(0, \tau_2^2)$$

$$L3: \gamma_{00k} = \delta_{000} + \delta_{001}local_authority_k + \delta_{001}TX_k + \varsigma_{0k}, \quad \varsigma_{0k} \sim N(0, \tau_3^2)$$

Longitudinal followup analyses (12 month only) - Secondary outcomes

Secondary outcomes will be analysed similarly, but

$$L1: g(Y_{ijk}) = \beta_{0jk} + \beta_{1jk}time_{ijk} + r_{ijk}, \quad r_{ijk} \sim N(0, \sigma^2_{|X})$$

$$L2: \beta_{0jk} = \gamma_{00k} + \mu_{0jk}, \quad \mu_{0jk} \sim N(0, \tau_2^2)$$

$$\beta_{1jk} = \gamma_{100} + \mu_{1jk}, \quad \mu_{1jk} \sim N(0, \tau_2^2)$$

$$L3: \gamma_{00k} = \delta_{000} + \delta_{001}local_authority_k + \delta_{001}TX_k + \varsigma_{0k}, \quad \varsigma_{0k} \sim N(0, \tau_3^2)$$

For the remaining secondary outcomes, their effect sizes will be reported as either Hedges' g (same as primary outcome) or rate ratios (other secondary outcomes, exponentiated parameter estimates), given that generalized linear mixed effects models with log link function are used to model the data and that the measures are positively scored integers with some amount of skew anticipated (Barnett and Dobson, 2008).

Mediation analyses (12 months report only)

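### The multiple imputation model makes no provision for family clustering, so the imputed analyses of parent-reported outcomes will have standard errors slightly too small

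*SAP*

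**What the plan says.** **Design.** Under Sample size, the SAP puts the mean number of parents in each family at no more than 1.5. For the clustering, it expects "a high degree of correlation among parents/carers from the same family, so also allow for an ICC=0.5". It assumes a baseline to follow-up correlation of 0.5. On attrition it says "The sample size is then inflated to account for 20% of families being lost to follow-up", and ties this to the 12-month follow-up.

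**Analysis model.** Under Primary analysis (6 month), the outcome is fitted by a linear mixed model with baseline SDQ, local authority, trial arm and a family random intercept, in randomised participants who provide outcome data.

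**Imputation.** Under Missing data, a full multiple imputation strategy starts when more than 5% of data in the primary model is missing, or more than 10% of a single variable. It uses chained equations in mice with 10 imputed datasets. Under Missing data in item level data, each item's "imputation model will use other items and covariates specified in the primary analysis model as predictors". For the primary outcome, "we will use an ordinal regression within the imputation model for each item"; for secondary outcomes the item model is logistic or ordinal. Total scores are then built from the imputed items, the primary and secondary models are fitted, and results are pooled by Rubin's rules.

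The imputation text mentions no family identifier, co-parent score, two-level method or family-wise layout. mice is the only imputation package in the software list. The protocol's text on missing data does not mention clustering.

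**The concern.** Family enters the primary model as a random effect, not as a covariate. An imputation model built from other items and the model's covariates therefore leaves family out. The imputed values are then analysed by a model that estimates the family variance, so the two models are incompatible.

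This has two consequences when a whole questionnaire is missing:

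- Two parents of the same lost family are imputed as independent given arm, baseline and local authority. The imputed data then show less family correlation than the real data, and the mixed model gives too small a standard error for a comparison randomised by family.
- If only one parent responds, that parent's score is not used to predict the other's. On the plan's figures, the co-parent's score (ICC 0.5) predicts about as well as the parent's own baseline (r = 0.5).

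At stake is the accuracy of the error bars in the plan's main check on missing data, and in any secondary parent-reported analysis run on imputed data.

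**Working it through.** **1. Inputs.** All are from the SAP's Sample size section: "an effect size to be detected of 0.35 with 90% power and a two-sided alpha of 0.05"; ICC 0.5; 1.5 parents per family; r = 0.5; 20% of families lost (at 12 months); 1:1 allocation by family.

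**2. The plan's own figure.**

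- Two-group comparison: n per arm = 2(1.960 + 1.282)²/0.35² = 171.6, so 172.
- Design effect: 1 + (1.5 − 1) × 0.5 = 1.25, giving 215.
- Baseline adjustment: 1 − 0.5² = 0.75, giving 161.25.
- Attrition: 161.25/0.8 = 201.6, so 202 per arm and 404 in total.

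The t-based version gives 406, or 408 with rounding up at each step. The stated 412 is within 2% of 404, and power at 412 is 0.905-0.907. The inputs can therefore be carried forward.

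**3. What happens to the ICC.** If the imputation model has no family term, only pairs with both parents observed keep the correlation of 0.5. Pairs with an imputed member have about zero, given the covariates.

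- 20% of whole families lost: 0.80 × 0.5 = 0.40.
- 20% of parents lost singly: 0.80² × 0.5 = 0.32.

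**4. Simulation with a true effect of 0.35.** There were 1,500 trials per setting, each with 275 families (138 with two parents, 137 with one), six local authorities and 10 imputations. The analysis was a mixed model with a family intercept, pooled by Rubin's rules. Assumptions not in the documents are the split of family sizes, missingness completely at random, and continuous scores in place of summed ordinal items. In each pair of figures, the first is imputation without family and the second is family-aware imputation.

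| Missing | Mean SE / empirical SD | Coverage (%) | ICC in imputed data |
|---|---|---|---|
| 10% of families | 0.96 / 0.99 | 94.0 / 94.9 | 0.45 / 0.50 |
| 20% of families | 0.97 / 1.01 | 94.3 / 95.6 | 0.40 / 0.50 |
| 20% of parents | 0.955 / 0.986 | 93.6 / 94.5 | 0.32 / 0.49 |
| 40% of families | 0.88 / 0.97 | 92.2 / 94.4 | 0.30 / 0.50 |
| 40% of parents | 0.92 / 0.97 | 92.9 / 94.5 | 0.18 / 0.50 |

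At 20% loss the mean SEs are 0.1060 against 0.1107 for whole families (4% smaller without family) and 0.1046 against 0.1072 for single parents (2% smaller). The mean estimate lay between 0.346 and 0.357 in every setting, so there is no sign of bias. The ICCs match step 3.

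**5. Larger run with no true effect.** With 6,000 trials per setting and 20% missing, imputation without family gave SE / empirical SD of 0.96-0.97 and type I error of 5.9-6.1%. The ICC was 0.40 (families lost) and 0.32 (parents lost singly). The Monte Carlo standard error at 5% is √(0.05 × 0.95/6000) = 0.28 points, so chance alone would give about 4.4-5.6%. The excess is small but real.

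**6. Effect-size correction.** The SAP's Hedges formula contains √[1 − 2(n − 1)ρ/(N − 2)]. With n = 1.5 and N = 412 this is 0.9994 at ρ = 0.50 and 0.9996 at ρ = 0.32. The fall in the ICC does not matter there.

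**The case against.** The case for leaving the plan alone has several parts.

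- **The SAP never says single-level.** It also does not say whose items are the other items. But nothing in the text brings in the co-parent, so an analyst following it would leave family out. The fair statement is that no provision is made.
- **Reach is limited.** Imputation is listed under Sensitivity analyses, and the available-case primary model keeps its family intercept. The protocol expects one adolescent per household, so self-reported outcomes have no parent clustering to preserve. This stands.
- **Partly missing questionnaires are largely safe.** If a parent skips a few items, that parent's remaining items carry most of the family correlation. This stands, and the fault mainly concerns wholly missing questionnaires.
- **The simulations are not the SAP's exact procedure.** They impute a continuous total, not ordinal items. The mechanism in step 3 does not depend on that, but the exact percentages do.
- **Noise.** With 1,500 trials, coverage carries a Monte Carlo margin of about 1.1 points, so the 94.3% for lost families proves little alone. The 6,000-trial run settles the direction.

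A reader might infer four stronger things that the material does not support:

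- **The 5% trigger is certain to be met at the primary endpoint.** The 20% is a 12-month figure and no 6-month figure is given. Crossing 5% is likely, but it is an assumption.
- **The trial's reported ICC will be wrong.** The SAP reports the ICC from the two-level model and does not say that it comes from imputed data.
- **The main test is seriously inflated.** It is not affected.
- **Family-aware imputation brings a marked gain in precision.** With parents lost singly at 20%, the empirical SD is 0.1087 against 0.1095, less than 1% smaller.

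**Conclusion.** The point holds, and it is minor. As written, the imputation model leaves out a family correlation that the design puts at 0.5 and that the analysis model estimates. At an assumed 20% missing, pooled standard errors in the imputed analyses of parent-reported outcomes are about 3-4% too small. Type I error is about 6% instead of 5%, and the ICC in the imputed data is about 0.3-0.4 instead of 0.50. The effect is modest because families average only 1.5 parents. It grows with loss: at 40%, coverage without family falls to 92-93%.

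These sizes rest on missingness completely at random, continuous scores, about half of families having two parents, and whole questionnaires being missing.

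**What to change.** State in the SAP's Missing data section that the imputation respects family, by one of two routes:

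- two-level imputation with family as the cluster; or
- the co-parent's scores as predictors, with two-parent families imputed in wide format (one row per family, each parent's scores predicting the other's). One-parent families are handled without a second parent, and none is ever created for them.

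In either case, name trial arm explicitly as a predictor. Also say whether the imputation above the 5% trigger is only a sensitivity analysis or also applies to the main results, since Sensitivity analyses and Missing data can be read differently on this.

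The cost is more programming and a larger imputation model. The wide format needs care to keep one- and two-parent families apart. For the two-level route, the analyst must check that the listed software can fit it to ordinal items. No new data are needed.

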- Exploring the impact of different levels of intervention receipt (adherence) and fidelity of intervention delivery on outcomes. We will use either two-stage least squares instrumental variables regression or inverse probability of treatment weighting methods to examine the effect of the intervention in those who receive varying levels of it.

All analyses will be checked subject to satisfying required assumptions. These checks include:

1. Linearity – plotting residuals vs predictor(s). If a structure is present, then transformation or an alternate model specification is required (i.e. GLM).
2. Homogeneity of variance – variance of the residuals across groups is the same. There is scope to fit models allowing for heterogeneous groups, but the setup is different (Generalized linear mixed model - GLMM).
3. Residuals are approximately normally distributed – plotting QQ plot

If distributional assumptions are not satisfied, as appropriate, a generalized linear model with alternate link function will be used. Alternatively, data transformation could be used but use of the GLM is preferable.

Longitudinal follow-ups (12 months post-randomisation)

We will fit linear mixed models, accounting for repeated post-randomisation measures (6- and 12-months post-randomisation) within participants, adjusting for baseline measures, adolescent factors (age, gender, parents in household), local authority and practitioners to investigate the overall effect of the intervention on post-randomisation measures.

Exploratory mediation analyses may also be carried out to examine variables at 6 months that may mediate intervention effects between baseline and 12-month follow-up. Any such analyses will be specified once a final Logic Model is confirmed. We would, however, anticipate

a theoretically derived set of questions relating to changes in parenting practices to mediate the impact of intervention on SDQ outcomes.

Analyses described in this section will be reported in the 12-month post-randomisation report only.

Withdrawal & participant retention

Withdrawal

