Baseline and 6-month follow up data will only be used in the primary analysis. The 12 month follow up data will be used both in the addendum primary analysis and in an additional follow up analysis including all three time points in a linear mixed model (see section 6.4 – longitudinal follow up analyses). The SDQ consists of 25 items which are each scored on a 3-point Likert scale (0, 1, 2). Externalising scores - Ranges from 0-20 and is generated by summing the scores of the conduct and hyperactivity subscales.

List of secondary outcomes

Secondary outcome measures include:

- Emotional and behavioural difficulties and prosocial behaviour: the Parent report and adolescent self-report versions of the Strengths and Difficulties Questionnaire (SDQ) will be used (including internalising, externalising, peer relationship, and prosocial behaviours). The SDQ is a robust and well-validated measure of behavioural and emotional problems (Deighton et al., 2014); measured over the preceding 6 months.
- Parenting practices: Parenting Scale Adolescent version (PSA, parent completed) is a short form of the Parenting Scale (Irvine et al., 1999) which assesses dysfunctional discipline practices in parents. It is an adaptation of the Parenting Scale (Arnold, et al., 1993) for parents of adolescents
- Interparental outcome - Dyadic Adjustment Scale (DAS-7) is a 7-item measure (Sharpley & Cross 182; Hunsley et al., 2001) assessing the relationship quality of couples. The DAS-7 assesses relationship satisfaction and the degree to which the couple agrees on matters of importance to the relationship.
- Parent mental health – the Kessler Psychological Distress Scale (Kessler 6) is a six-item screening tool for serious mental illness in the general population (Kessler et al., 2003). It will be completed by parents.
- Parent Wellbeing - The Warwick-Edinburgh Mental Well-being Scale (SWEMWBS) is a measure of mental wellbeing (Tennant et al., 2007). The short (7 item) version will be completed by parents.
- Conflict Behavior Questionnaire (CBQ-20) (Robin & Foster, 1989) assesses adolescent-parent communication, conflict and relations. Both the adolescent and parent report versions will be completed.
- Child-parent relationship – the Closeness subscale of the Child-Parent Relationship Scale (CPRS, short form) measures (Pianta, 1995) will be completed by parents.

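### The SAP's longitudinal model omits the baseline score that the Protocol says it adjusts for, and the SAP does not settle whether baseline is an outcome row

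*SAP*

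**What the plan says.** **SAP, Additional analyses, longitudinal follow-up (12 month only).** The model is described as "accounting for repeated post-randomisation measures (6- and 12-months post-randomisation) within participants", with local authority as the only adjustment: "within participants, adjusting for local authority to investigate the overall effect of the intervention". In the equations, level 1 has an intercept and time. The time slope has a fixed mean and a participant-level random deviation, with no arm term. Arm enters only through the intercept: "\delta_{000} + \delta_{001}local_authority_k + \delta_{001}TX_k". That line gives local authority and arm the same coefficient symbol. There is no baseline score and no arm-by-time term. The same structure, with a link function, is printed for the secondary outcomes.

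**SAP, Timing, units, and derivation of primary.** The 12-month data will be used in a repeat of the primary analysis and "in an additional follow up analysis including all three time points in a linear mixed model".

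**Protocol, Longitudinal follow-ups (12 months post-randomisation).** The same analysis is specified as "adjusting for baseline measures, adolescent factors (age, gender, parents in household), local authority and practitioners".

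The SAP's other models for the SDQ arm comparison (primary, practitioner sensitivity, instrumental-variable stage 2, moderation, mediation) all carry a baseline term. The SAP gives no reason for leaving it out here.

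**The concern.** Two things are unsettled: whether baseline is used at all, and if so, whether as a covariate or as an outcome. An analyst could follow the SAP faithfully in two ways.

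- **6- and 12-month outcomes, as in the longitudinal section.** Baseline is ignored. The comparison is valid but gives up precision that the Protocol specified and that costs nothing.
- **All three time points as outcome rows, as the outcome definition can be read.** The single arm coefficient is a constant shift across baseline, 6 and 12 months. Randomisation makes the expected baseline difference zero, so the coefficient mixes that zero with the follow-up effects. It is then no longer the effect on post-randomisation scores that the section says it is after.

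At the planning values the two implementations target coefficients that differ by a third. The choice should not be left until the data are in hand.

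**Working it through.** **The plan's own figure.** Neither document gives a figure for the longitudinal model, so I start from the sample size. Inputs (SAP, Sample size): d = 0.35, 90% power, two-sided 0.05, ICC 0.5, 1.5 parents per family, r = 0.5, 20% of families lost.

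- Per arm before adjustment: 2 × ((1.960 + 1.282)/0.35)² = 171.5, so 172.
- Design effect: 1 + (1.5 − 1) × 0.5 = 1.25. Baseline-adjustment factor: 1 − 0.5² = 0.75.
- 172 × 1.25 × 0.75 = 161.25; divided by 0.8 this is 201.6, so 202 per arm and 404 in total. The stated 412 is within 2%.
- Effective number per arm at the stated size: 206 × 0.8/1.25 = 131.84.

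Below, SE = √(2v/131.84), where v is the variance of the per-person quantity compared between arms, in SD² units. I assume the same correlation r between every pair of visits and a constant effect of 0.35 at 6 and 12 months.

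**Reading A: 6 and 12 months as outcomes.** Without baseline, v = (1 + r)/2. With baseline as a covariate, v = (1 + r)/2 − r².

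| r | v without | v with | SE without | SE with | SE ratio |
|---|---|---|---|---|---|
| 0.50 | 0.75 | 0.50 | 0.107 | 0.087 | 1.22 |
| 0.74 | 0.87 | 0.3224 | 0.115 | 0.070 | 1.64 |
| 0.84 | 0.92 | 0.2144 | 0.118 | 0.057 | 2.07 |

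The values 0.74 and 0.84 are the ends of the SDQ test-retest range that the SAP quotes. Power at r = 0.5 is 90.7% without baseline and 98.0% with it.

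**Reading B: baseline, 6 and 12 months as outcome rows, arm main effect only.** The generalised least squares weights are w = V⁻¹1/(1′V⁻¹1). Under equal correlations each visit has weight 1/3, so the expected coefficient is (0 + 0.35 + 0.35)/3 = 0.233, which is 67% of 0.35. Here v = (1 + 2r)/3 = 0.667 at r = 0.5 and SE = 0.1006. Power is Φ(0.233/0.1006 − 1.96) = Φ(0.36), about 64%. At r = 0.74 and 0.84 it is 55% and 52%.

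The printed random slope would move more weight to baseline. The documents give no slope variance. As an illustration, take time coded 0, 1, 2, with intercept and residual variances of 0.5 each. Slope variances of 0.05 to 0.25 then leave 58% to 42% of the effect.

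**Simulation check.** 600 replicates, 275 families of one or two parents, ICC 0.5, r = 0.5, equal correlations, 20% of families lost after baseline:

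- Reading A without baseline: mean coefficient 0.351, SE 0.108, power 91%.
- Reading A with baseline: 0.351, SE 0.088, power 97.5%.
- Reading B: 0.199 (57% of 0.35), power 54%. Lost families still contribute a baseline row, which pulls the coefficient down further.

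**Random slope with two visits.** Two visits per participant give three moments: two variances and one covariance. Random intercept, random slope, their covariance and a residual make four parameters, so that version is not identified. With independent effects and time coded 0 and 1, var(6) = τ₀² + σ², cov = τ₀² and var(12) = τ₀² + τ₁² + σ². That is three equations in three unknowns, which can be solved. The SAP prints no covariance and uses one variance symbol for both random effects, so the intended structure is unclear.

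**The case against.** The strongest reply is that the section defining the model names 6 and 12 months only and targets post-randomisation scores, as the Protocol does. On that reading the estimate is unbiased. At r = 0.5, the variance factor for an unadjusted two-visit mean, (1 + 0.5)/2 = 0.75, equals the 1 − r² = 0.75 used to size the trial, so power stays at about the planned 90%. The sentence about all three time points could simply mean that baseline enters as a covariate. And this is an additional analysis. All of that stands, except that the printed equations do not include baseline as a covariate, so the benign reading of that sentence is not what the SAP specifies.

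A reader might infer more than the documents support:

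- **That the planned estimate is biased toward zero.** This follows only if baseline is an outcome row, which neither document states outright.
- **That the model is not identified.** This needs an intercept-slope covariance that the SAP does not print.
- **That the plan cannot show whether an effect lasts to 12 months.** The SAP repeats the primary analysis, with its baseline covariate, at 12 months. For an overall effect across 6 and 12 months, an arm main effect is a legitimate average, and the Protocol specifies no arm-by-time term either.
- **That every secondary outcome is affected.** The delinquency measure is not collected at 6 months, so it has no repeated follow-up to model.

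**Conclusion.** The omission of baseline and the conflict over time points are both real. The cost depends on the reading. With 6- and 12-month outcomes it is precision only: an SE 22% larger than with baseline adjustment at r = 0.5, and 64% to 107% larger at r = 0.74 to 0.84. With baseline as an outcome row it is dilution to about two thirds of a constant effect, with power of about 64% at r = 0.5, under equal correlations and complete data. The sizes rest on those correlations, a constant effect, and the plan's ICC, family size and loss. They apply to continuous outcomes on the identity link. The downward direction under the second reading was the same in every case computed.

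The reach is the longitudinal analysis in the 12-month report, for the primary outcome and the secondary outcomes measured at both 6 and 12 months. The 6-month primary analysis, the sample size of 412 and the baseline-adjusted repeat at 12 months are untouched. It should be fixed, but it does not put the trial's main conclusion at risk.

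**What to change.** Before the 12-month analysis:

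1. In the SAP's longitudinal section, state that the outcomes are the 6- and 12-month scores, and add the outcome's own baseline score as a covariate, as the Protocol specifies.
2. Keep random intercepts for parent and family, and drop the participant random time slope.
3. Give local authority and arm different coefficient symbols.
4. In the SAP's section on timing and derivation of the primary outcome, reword the sentence so that baseline enters as a covariate.
5. Optionally, add an arm-by-time term if the 6- and 12-month effects are to be reported from the same model.

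The cost is an edit to the longitudinal text and equations, including the copy for secondary outcomes, and one sentence elsewhere. No new data are needed, because baseline scores are already collected.
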